10.1.3.2 Handling of Biological Specimens

PK samples obtained from subjects will be stored at the centralized clinical laboratory until ready for PK analyses by the bioanalytical laboratory using a validated method.

10.2 Appropriateness of Measurements

The efficacy and safety assessments planned for this study are widely used and generally recognized as reliable, accurate, and relevant to the disease condition.

11 STATISTICAL METHODS AND DETERMINATION OF SAMPLE SIZE

11.1 Subject Populations

Five populations will be considered in the statistical analysis of the study, as specified below.

11.1.1 Screened Population

The Screened Population will consist of all subjects who underwent a Screening Visit and received a subject number, and signed the ICF.

11.1.1.2 Randomized Population

The Randomized Population will consist of all subjects in the Screened Population who are randomized to a treatment group in the study.

11.1.1.3 Safety Population

The Safety Population will consist of all subjects in the Randomized Population who took at least one dose of study medication.

CONFIDENTIAL

11.1.1.4 Modified Intent-to-Treat (mITT) Population

The modified Intent-to-Treat (mITT) Population is defined as all subjects who are randomized and receive at least one dose of study medication, and have both baseline and at least one postbaseline primary efficacy measure (ie, PARS severity score). The mITT population will be used for all of the efficacy analyses.

11.1.1.5 Pharmacokinetic Population

The PK Population is defined as all subjects in the Safety Population with at least one evaluable plasma concentration of escitalopram or S-demethylcitalopram.

11.2 Disposition

The number of subjects in the Screened Population will be summarized overall by study center. The number of subjects in the Randomized, Safety, and mITT Populations will be summarized by treatment group and study center. Subjects whose disposition status was impacted by the COVID-19 pandemic will also be summarized.

Screen failures (ie, subjects who were screened but not included in the Randomized Population) and the associated reasons for failure will be tabulated overall. The reasons for premature discontinuation from the double-blind treatment period as recorded on the termination pages of the eCRF will be summarized (number and percentage) by treatment group for the Safety Population.

The number and percentage of subjects with significant protocol deviations will be summarized overall and by treatment group for the Randomized Population. Deviations related to the following categories will be included:

- inclusion or exclusion criteria
- withdrawal criteria
- treatment or dose
- concomitant medications

These and any additional significant protocol deviations will be reviewed and documented before database lock and unblinding of treatment codes.

Protocol deviations that occur due to COVID-19 will be summarized and listed separately.

CONFIDENTIAL

11.3 Demographic and Other Baseline Characteristics

Demographic parameters (eg, age, age group [7-11 vs. 12-17 years], sex, race, ethnicity, weight, weight z-score, height, height z-score, BMI, BMI z-score) and other baseline characteristics will be summarized by treatment group for the Safety and mITT Populations. Descriptive statistics (n, mean, standard deviation, minimum, median, and maximum) will be presented for continuous variables, and frequency distributions (counts and percentages) will be presented for categorical variables.

Medical history terms will be encoded using the latest available Medical Dictionary for Regulatory Activities (MedDRA) dictionary. Summaries of medical history will be produced by system organ class (SOC) and preferred term (PT).

Psychiatric history and results from the MINI Kid will be summarized descriptively.

Prior and concomitant medications, including prior treatment for GAD, will be coded using the latest available WHO Drug dictionary. Drug classes and preferred names will be summarized by randomized treatment.

11.4 Extent of Exposure and Treatment Compliance

11.4.1 Extent of Exposure

11.4.1.1 Investigational Product

Total exposure to double-blind investigational product for the Safety Population during the double-blind treatment period will be summarized, calculated as the number of days from the date of the first dose of double-blind investigational product taken to the date of the last dose taken through the Week 8 End of Treatment or Early Withdrawal Visit, inclusive. Descriptive statistics (n, mean, standard deviation, minimum, median, and maximum) will be presented by treatment group. Similarly, the treatment duration in the down taper period, defined as the first dose in the down taper period to the last dose in the down taper period, inclusive, will be summarized. The total duration of double-blind investigational product exposure, defined as the sum of the treatment duration through Week 8 and the duration in the down taper period will be summarized.

The number and percentage of subjects who had their dosage escalated at Week 2 from 10 mg/day to 20 mg/day will be summarized by treatment group. The denominator will be the number of subjects who had study medication dispensed at Week 2. Similarly, the number and percentage of subjects who had their dosage escalated at Week 4 from 10 mg/day to 20 mg/day will be summarized by treatment group. The number of subjects who required a dose reduction from 20 mg/day to 10 mg/day will be summarized by treatment group. The number of days from first date of escalation to 20 mg/day to the dose reduction will be summarized using descriptive statistics.

CONFIDENTIAL

The weekly and overall mean daily dose of investigational product will be summarized by treatment group for the Safety Population.

11.4.1.2 Prior and Concomitant Medication

Prior medication is defined as any recorded medication taken before the date of the first dose of double-blind investigational product. Concomitant medication is defined as any recorded medication used on or after the date of the first dose of double-blind investigational product. A medication may be classified as both a prior medication and concomitant medication.

Prior and concomitant medications, used for treatment of GAD and for other indications, will be summarized by the number and proportion of subjects in each treatment group receiving each medication within each therapeutic class for the Safety Population. Multiple medication use by a subject will only be counted once. Any recorded medications started after last dose of double-blind investigational product will not be summarized but will be included in listings.

11.4.2 Measurement of Treatment Compliance

Dosing compliance for a specified period will be defined as the total number of capsules actually taken by a subject during that period divided by the number of capsules prescribed to be taken for the same period multiplied by 100. This information will be obtained from the investigational product record of the subject's eCRF.

The total number of capsules actually taken during a specific time period is calculated based on the study medication record. The number of capsules prescribed to be taken for a specific treatment period will be calculated by multiplying the number of days in that period by the number of capsules to be taken per day.

Descriptive statistics for investigational product compliance will be presented by treatment group for each period between 2 consecutive visits, as well as for the entire double-blind treatment period, the period from first dose to the Week 8 End of Treatment or Early Withdrawal Visit, and the down taper period.

11.5 Efficacy Analysis

The efficacy analyses will be based on the mITT Population. Baseline for efficacy is defined as the last non-missing efficacy assessment recorded at or before the date of the first double-blind dosing. All statistical tests will be 2-sided hypothesis tests performed at the 5% level of significance. For efficacy analyses in which study center is a factor, a small center will be defined as a center with less than 2 subjects in at least 1 treatment group in the mITT Population. A pooling algorithm for the pooling of small centers will be specified in the statistical analysis plan (SAP). By-visit analysis based on the

CONFIDENTIAL

mixed-effects model for repeated measures (MMRM) using the observed case approach will be performed for all continuous efficacy parameters.

11.5.1.1 Primary Efficacy Analysis

The primary efficacy endpoint is the change from Baseline to Week 8 in the PARS severity score.

The PARS severity score for GAD is assessed for all symptoms identified in the generalized anxiety section of the PARS symptom checklist. The PARS severity score for GAD will be derived by summing 5 of 7 severity/impairment/interference items (2, 3, 5, 6, and 7).

The primary analysis will be performed using an MMRM with treatment group, age group strata (7-11 vs. 12-17 years), sex, study center, visit, and treatment group-by-visit interaction as the fixed effects and the baseline value and baseline value-by-visit interaction as the covariates. An unstructured covariance matrix will be used to model the covariance of within-subject scores. The Kenward-Roger approximation¹⁶ will be used to estimate denominator degrees of freedom for the unstructured covariance matrix. If the model convergence for the unstructured covariance matrix fails, then the Fisher scoring algorithm will be used to provide better initial values of the covariance parameters. In the event that the model still does not converge after using those initial values, simplified covariance structures will be used to fit the model in the following order until the model converges: (1) ante-dependence, (2) heterogeneous autoregressive, (3) Toeplitz, and (4) compound symmetry. If a structured covariance is used, then a robust sandwich estimator will be used for estimating the variance of the treatment effect estimate.

The MMRM analysis will be performed based on all post-baseline scores using only the observed cases without imputation of missing values.

The significance test for the difference in means at Week 8 will be based on least squares (LS) means using a 2-sided α of 0.05. Differences between treatments at the other post-baseline visits will also be estimated based on LS means.

Sensitivity analyses will be conducted on the primary efficacy endpoint to assess the missing at random assumption of the MMRM model and the impact of COVID-19 using remote home assessments. Details will be provided in the SAP.

CONFIDENTIAL

11.5.1.1.1 Estimand for the Primary Efficacy Analysis

The following describes the estimand approach for the primary efficacy analysis described in ICH E9 (R1) (2017)¹⁷.

Target Population

As noted above in [Section 11.5](#), the target population is the mITT population.

Variable

The variable is the same as the definition of the primary efficacy analysis described in [Section 11.5.1.1](#).

Accounting for Intercurrent Events

The primary analysis will treat measurements after study withdrawal as missing in the MMRM modeling, leading to an estimate of the treatment effect while on treatment. The impact of the missing at random assumption of MMRM will be assessed using 2 different approaches. The first will be a simple last observation carried forward (LOCF) approach. The second will be a sensitivity analysis using a pattern-mixture model. The details of this sensitivity analyses will be provided in detail in the SAP.

Population-level Summary

The population-level summary for the primary endpoint is the difference in primary variable means between the escitalopram group and placebo, while remaining on the study treatment.

11.5.1.2 Secondary Efficacy Parameters

Inferential testing for the secondary endpoints will be reported with nominal p-values. No adjustments for multiplicity will be made. All confidence intervals will be 2-sided 95% confidence intervals, unless stated otherwise.

The secondary efficacy endpoints are as follows:

- Response rate on the PARS at acute treatment endpoint (Week 8)
 - Response is defined as a 50% improvement on the PARS severity score for GAD.
- Remission rate on the PARS at acute treatment endpoint (Week 8)
 - Remission is defined as PARS severity score for GAD ≤ 8 (using 6 PARS items: 2, 3, 4, 5, 6, and 7)
- Change on the CGI-S from baseline to acute treatment endpoint (Week 8)

CONFIDENTIAL

- Remission rate on CGI-S at acute treatment endpoint (Week 8).
Remission rate is defined as the percentage of subjects having a CGI-S score ≤ 2 at endpoint.
- Change on the CGAS from baseline to acute treatment endpoint (Week 8)
 - Remission rate on the CGAS at acute treatment endpoint (Week 8).
Functional remission is defined as CGAS > 70 .
- COVID-19 impact assessment score at each visit.

The response rate of the PARS will be analyzed using a repeated measures model for categorical outcomes. Modeling will be completed using a categorical MMRM (MMRM-CAT) approach, in which a pseudo-likelihood-based repeated measures analysis will be used and implemented in SAS procedure GLIMMIX. A binary distribution with logit link will be used for the dependent variable. Classification variables for treatment, age group, sex, visit (as a categorical variable), treatment-by-age group interaction, treatment-by-sex interaction, treatment-by-visit interaction, and treatment-by-age group-by-sex interaction, and baseline score as a covariate will be considered in the modeling.

11.5.1.2.1 Analysis of Remission in PARS

The remission rate on the PARS will be analyzed using the same MMRM-CAT as the response rate on the PARS.

11.5.1.2.2 Change on the CGI-S from Baseline to Acute Treatment Endpoint (Week 8)

The change in the CGI-S will be analyzed using the same methodology described for the primary efficacy endpoint. The analysis of the remission rate for the CGI-S will use the same methodology described for the analysis of the response rate on the PARS.

11.5.1.2.3 Change on the CGAS from Baseline to Acute Treatment Endpoint (Week 8)

The change in the CGAS will be analyzed using the same methodology described for the primary efficacy endpoint. The analysis of the remission rate for the CGAS will use the same methodology described for the analysis of the response rate on the PARS.

11.5.1.2.4 COVID-19 Impact Assessment Score at each Visit

The COVID-19 impact assessment score will be summarized at each visit.

CONFIDENTIAL

11.6 Safety Analysis

The safety analysis will be performed for the double-blind treatment period and double-blind down taper period separately using the Safety Population. The safety parameters will include AEs, clinical laboratory parameters, vital sign measurements, and ECG parameters. For each safety parameter, the last assessment made before the first dose of double-blind investigational product will be used as the baseline for all analyses of that safety parameter.

Safety data collected outside of planned visit windows but within allowance limits (up to 1 week late for Visits 7 and 8) will be included in the summary tables. Safety data collected outside of planned visit windows and outside of the allowance limits (>1 week to 6 weeks late for Visits 7 and 8) will be listed, but will not be included in the summary tables. Subgroup analyses may be performed to assess the impact of COVID-19 on the safety analyses.

The safety endpoints during the double-blind treatment period are as follows:

- Incidence of treatment-emergent adverse events (TEAEs).
- Observed values and change from baseline in vital signs (blood pressure, pulse rate, temperature, respiration rate, height, weight, BMI, height percentile, weight percentile, and BMI percentile); incidence of vital sign potentially clinically significant (PCS) values.
- Observed values and changes from baseline in ECG intervals and interpretation; incidence of ECG PCS values.
- Observed values and changes from baseline in clinical laboratory assessments (hematology, chemistry, and urinalysis); incidence of clinical laboratory PCS values.
- Incidence of suicidal ideation and/or suicidal behavior as determined by the C-SSRS.

11.6.1.1 Adverse Events

AEs will be coded to an SOC and PT using the latest available version of MedDRA. An AE (classified by PT) not present before the date of the first dose of the double-blind treatment period or during the double-blind down taper period or that was present before the first dose but increased in severity or seriousness will be considered a TEAE. An AE that starts more than 30 days after the date of the last dose of double-blind investigational product will not be counted as a TEAE.

An AE that starts during the double-blind down taper period or that increases in severity or seriousness during the double-blind down taper period will be considered a newly emergent AE (NEAE). The NEAEs during the double-blind down taper period will be summarized by SOC, PT, and treatment group for all subjects who enter the double-blind down taper period.

CONFIDENTIAL

The number and percentage of subjects reporting TEAEs in each treatment group will be tabulated by SOC and PT; by SOC, PT, and severity; and by SOC, PT, and causal relationship to the investigational product. If more than one AE is coded to the same PT for the same subject, the subject will be counted only once for that PT using the most severe and most related occurrence for the summarization by severity and by causal relationship to the investigational product, respectively.

The distribution of TEAEs by severity and causal relationship to the investigational product will be summarized by treatment group. The incidence of common ($\geq 2\%$ of subjects in any treatment group) TEAEs during the double-blind treatment period will be summarized by PT and treatment group.

An SAE that occurred between the date of the first dose of double-blind investigational product and 30 days after the date of the last dose of double-blind investigational product in the study, inclusive, will be considered an on-therapy SAE. The incidence of SAEs and AEs leading to premature discontinuation of the study will also be summarized by study period (separately for double-blind treatment period and double-blind down taper period), SOC, PT, and treatment group. Listings will be presented for subjects with SAEs, subjects with AEs leading to premature discontinuation, and subjects who died. All subjects with SAEs, including those reported during the screening period or more than 30 days after the date of the last dose of the double-blind investigational product, and subjects discontinuing due to AEs before the start of double-blind investigational product will be included in these listings.

Each AE summary described above will be presented as all AEs, AEs that are associated with the COVID-19 pandemic (as determined by the investigator), and AEs that are not associated with the COVID-19 pandemic. AEs associated with the COVID-19 pandemic will be listed separately.

11.6.1.2 Vital Signs

Descriptive statistics for vital signs (ie, blood pressure, pulse rate, temperature, respiration rate, height, weight, BMI, height percentile, weight percentile, and BMI percentile) and changes from baseline values at each visit and at end of study will be presented by treatment group. Height, weight, and BMI z-scores will be calculated based on CDC growth charts.

Vital sign values will be PCS if they meet both the observed-value criteria and the change from baseline-value criteria. The criteria for PCS vital sign values will be detailed in the SAP. The percentages will be calculated relative to the number of subjects with baseline values and at least one postbaseline assessment. The numerator will be the total number of subjects with available baseline values and at least one PCS postbaseline value. A supportive listing of subjects with PCS postbaseline values will be provided, including the subject identification (SID) number, study center number, and

CONFIDENTIAL

baseline and postbaseline values. A listing of all AEs for subjects with PCS vital sign values will also be provided.

11.6.1.3 Electrocardiograms

Descriptive statistics for ECG parameters (ie, ventricular heart rate, RR interval, PR interval, QRS interval, QT interval, and QTc interval) and changes from baseline values at each assessment time point will be presented by treatment group. The QTc interval is calculated using both the Bazett ($QTcB = QT/(RR)^{1/2}$) and Fridericia ($QTcF = QT/(RR)^{2/3}$) corrections. The number and percentage of subjects with PCS postbaseline ECG values will be tabulated by treatment group. The criteria for PCS ECG values will be detailed in the SAP. The percentages will be calculated relative to the number of subjects with available non-PCS baseline values and at least one postbaseline assessment. The numerator will be the total number of subjects with available non-PCS baseline values and at least one PCS postbaseline value. A supportive listing of subjects with PCS postbaseline values will be provided, including the SID number, study center number, and baseline and postbaseline values. A listing of all AEs for subjects with PCS ECG values will also be provided.

A listing of subjects with postbaseline clinically significant ECG abnormalities, as reported by the investigator or by the central cardiologist, will also be provided.

The number and percentage of subjects with an increase >30 msec but ≤ 60 msec, and with an increase >60 msec in QTcB or QTcF will be tabulated. A supportive listing of subjects with postbaseline QTcB or QTcF increases >30 msec will be provided, including the SID number, study center, and all QTcB and QTcF values (including changes from baseline). A listing of all AEs for subjects with postbaseline QTcB or QTcF increases >30 msec will also be provided.

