10.1.2.6 Electrocardiogram

A 12-lead single trace ECG will be performed at the times outlined in the Schedule of Assessments in [Section 8.1.2](#) in a standardized manner (ie, after the subject has rested in the semi-supine position for at least 5 minutes). Measurements will include ventricular heart rate, RR interval, PR interval, QRS interval, QT interval, and QTc interval. The QTc interval will be calculated using both the Bazett correction ($QTcB = QT/(RR)^{1/2}$) and the Fridericia correction ($QTcF = QT/(RR)^{1/3}$).

The ECGs will be centrally read. The date and an overall interpretation of the ECG will be recorded in the eCRF. Any abnormalities will be assessed as clinically significant or not clinically significant and recorded on the eCRF.

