10.4 ELECTROCARDIOGRAM

Descriptive statistics for ECG parameters (heart rate, PR interval, QRS interval, RR interval, QT interval, and QTc interval) at baseline and changes from baseline values at each assessment time point will be presented by treatment group. The QTc interval is calculated using both the Bazett (QTcB = QT/(RR) $\frac{1}{2}$) and Fridericia (QTcF = QT/(RR) $\frac{1}{3}$) corrections. Only subjects with available baseline and at least 1 postbaseline assessment will be included in the summary.

Electrocardiographic parameter values are considered PCS if they meet or exceed the higher-limit PCS criteria listed in Table 10.4–1. The number and percentage of subjects with PCS postbaseline ECG values will be tabulated by treatment group. The percentages will be calculated relative to the number of subjects with available non-PCS baseline values and at least 1 postbaseline assessment. The numerator is the total number of subjects with available non-PCS baseline values and at least 1 PCS postbaseline value. A supportive listing of subjects with PCS postbaseline values will be provided, including the SID number, study center number, baseline, and all postbaseline (including non-PCS) values.

Table 10.4–1. Criteria for Potentially Clinically Significant Electrocardiographic Parameters

Parameter	Unit	Higher Limit
QRS interval	msec	≥ 150
PR interval	msec	≥ 250
QTcB	msec	> 460
QTcF	msec	> 450

QTcB = QT interval corrected for heart rate using the Bazett formula (QTcB = QT/(RR) $^{1/2}$); QTcF = QT interval corrected for heart rate using the Fridericia formula (QTcF = QT/(RR) $^{1/2}$).

bpm = beats per minute kg = kilogram, mmHg = millimeters of mercury hemoglobin.

Page 36 of 53

In addition, a listing of all AEs that occurred in subjects who had postbaseline PCS ECG values will be provided.

A listing of subjects with postbaseline clinically significant ECG abnormalities, as reported by the investigator or by the central cardiologist, will also be provided.

The number and percentage of subjects with an increase > 30 msec but ≤ 60 msec, and with an increase > 60 msec in QTcB or QTcF will be tabulated. A supportive listing of subjects with postbaseline QTcB or QTcF increases > 30 msec will be provided, including the SID number, study center number, and all QTcB and QTcF values (including changes from baseline). A listing of all AEs for subjects with postbaseline QTcB or QTcF increases > 30 msec will also be provided.

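### The Fridericia QT correction is printed with inconsistent exponents (1/3, 2/3 and, as extracted, 1/2), so the QTcF safety tables are not uniquely defined

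*Protocol*

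**What the plan says.** The Fridericia correction is written out in four places:

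- Protocol 10.1.2.6, on how the ECG is measured: "the Fridericia correction ($QTcF = QT/(RR)^{1/3", exponent 1/3. The same sentence gives Bazett as "the Bazett correction ($QTcB = QT/(RR)^{1/2", exponent 1/2.
- Protocol 11.6.1.3, on how the ECG is analysed: "Fridericia ($QTcF = QT/(RR)^{2/3}$) corrections", exponent 2/3.
- SAP 10.4, running text: "Fridericia (QTcF = QT/(RR) $\frac{1}{3}$) corrections", exponent 1/3.
- SAP 10.4, footnote to Table 10.4-1: "using the Fridericia formula (QTcF = QT/(RR) $^{1/2", exponent 1/2 as extracted. The footnote gives the same exponent for Bazett.

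Table 10.4-1 sets the limits for potentially clinically significant (PCS) values: above 450 msec for QTcF and above 460 msec for QTcB. PCS percentages are taken over the "number of subjects with available non-PCS baseline values and at least 1 postbaseline assessment", and the numerator carries the same baseline condition. QTcF also enters the change categories of more than 30 up to 60 msec and more than 60 msec; the latter reads "with an increase > 60 msec in QTcB or QTcF will be tabulated". Subject and adverse event listings follow from both sets of tables.

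SAP section 17.0 lists the departures from the protocol. It names only the handling of weight and height z-scores and states that there are no others.

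**The concern.** One named correction should have one formula. Here the two sections of the protocol disagree, and the SAP running text disagrees with its own table footnote. Section 17.0 of the SAP rules out reading any of this as a declared change of method.

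At a heart rate of 60 bpm the exponent makes no difference. Away from 60 bpm it changes every QTcF value, and with it the PCS counts, the change categories and the listings. Safety is part of the primary objective (protocol 7.1), and the protocol names QT prolongation among the ECG changes seen in overdose (10.1.2.2.5). QTcF is therefore an output that readers of the study report will look at.

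**Working it through.** The plan gives no QTcF result to reproduce, so this is a direct comparison of the printed formulas.

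**Inputs from the documents.** Exponents 1/3, 2/3 and 1/2; PCS limits of 450 msec (QTcF) and 460 msec (QTcB); change categories above 30 and above 60 msec; the non-PCS-baseline rule.

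**Assumptions, not in the documents.** RR is in seconds, so RR = 60/HR. Heart rates are 60-110 bpm, with 50 bpm added to show the direction below 60. The 1/3-based QTcF is taken between 380 and 440 msec.

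**Step 1: multiplier.** With QTc(e) = QT/RR^e, replacing exponent 1/3 by e multiplies QTcF by RR^(1/3 − e).

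**Step 2: value that reaches the limit.** The 1/3-based QTcF that reads 450 msec under exponent e is 450 × RR^(e − 1/3).

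| HR (bpm) | RR (s) | Multiplier, e = 1/2 | Multiplier, e = 2/3 | 1/3-based QTcF reading 450, e = 1/2 | Same, e = 2/3 |
|---|---|---|---|---|---|
| 50 | 1.200 | 0.970 | 0.941 | 463.9 | 478.2 |
| 60 | 1.000 | 1.000 | 1.000 | 450.0 | 450.0 |
| 70 | 0.857 | 1.026 | 1.053 | 438.6 | 427.5 |
| 80 | 0.750 | 1.049 | 1.101 | 428.9 | 408.9 |
| 90 | 0.667 | 1.070 | 1.145 | 420.6 | 393.1 |
| 100 | 0.600 | 1.089 | 1.186 | 413.3 | 379.5 |
| 110 | 0.545 | 1.106 | 1.224 | 406.8 | 367.7 |

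**Step 3: a mid-range value.** A 1/3-based QTcF of 400 msec at 80, 90, 100 and 110 bpm reads 440, 458, 474 and 490 under exponent 2/3, so it is over 450 from 90 bpm. Under 1/2 it reads 420, 428, 436 and 442 and never crosses. From the raw interval, QT 350 msec at 90 bpm gives 400.6 (1/3), 428.7 (1/2) and 458.6 (2/3).

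**Step 4: spurious change.** Hold the 1/3-based QTcF at 400 msec and let the heart rate rise from 70 to 90 bpm. Under 2/3 the reading moves from 421.1 to 457.9, a change of 36.8 msec and enough to enter the category above 30 msec. Under 1/2 it moves from 410.4 to 428.0, a change of 17.6 msec.

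**Step 5: exponent 1/2 against the two limits.** QTcF and QTcB become the same number. Any value above 450 and up to 460 msec is then PCS as QTcF and not PCS as QTcB.

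**Step 6: direction below 60 bpm.** At 50 bpm a 1/3-based QTcF of 460 msec reads 460 × 0.970 = 446 under 1/2 and 460 × 0.941 = 433 under 2/3. A value that should be flagged would be missed.

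**Step 7: the counting rule.** A subject whose baseline is inflated past 450 msec leaves both numerator and denominator. A subject inflated past it only after baseline is added to the numerator. The net effect on the PCS percentage can therefore go either way.

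**The case against.** The best defence is that the operative text is already consistent. The SAP is the more detailed document, and its sentence on how QTc is calculated has exponent 1/3, in agreement with the protocol's measurement section. Protocol 11.6.1.3 sets no limit itself and leaves the PCS criteria to the SAP. The ECGs are read centrally, the method is named as Fridericia throughout, and the same formula would apply to both arms. The 2/3 may never reach a program. This stands as a reason to expect correct output. It does not make the protocol's analysis section correct as printed.

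Extraction is the second defence. The SAP footnote exponent is a small superscript directly after the Bazett one, and the extraction visibly disturbed the layout around that table. The 1/2, and everything that follows from it, is unconfirmed until the source page is checked. The 1/3 and 2/3 in the protocol came through in the same clean notation, so that contradiction is firmer.

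A reader might also infer that both deviant exponents would push ordinary paediatric values over 450 msec, or that PCS counts would simply be inflated. The documents support neither. They give no expected heart rate, QT or QTcF for ages 7 to 17. Within 60-110 bpm exponent 1/2 does not take a value of 400 msec over the limit. The direction reverses below 60 bpm, and the baseline rule removes subjects as well as adding them.

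**Conclusion.** The inconsistency is real and the analysis formula in protocol 11.6.1.3 is wrong as written. Exponent 1/3 is the form the documents themselves repeat, and 1/2 is already assigned to Bazett.

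Under the stated assumptions, exponent 2/3 can take a QTcF of about 400 msec over the limit at 90 bpm or more. It can also create about 37 msec of false change for a rise from 70 to 90 bpm. Exponent 1/2, if it is truly on the page, crosses only from about 421 msec at 90 bpm or 413 msec at 100 bpm. Its firmer consequence is a QTcF that duplicates QTcB under a different limit. Both can hide prolongation below 60 bpm.

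The effect is confined to descriptive safety tables and listings. The primary efficacy analysis and the sample size are untouched. The point should be fixed before programming, but it does not threaten the trial's main conclusion.

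**What to change.** 1. State QTcF = QT/(RR)^(1/3), with RR in seconds, in protocol 11.6.1.3.
2. Check the footnote of SAP Table 10.4-1 against the source page. If it does print 1/2, correct it to the same formula.
3. Confirm in writing that the central ECG reader and the analysis programs use exponent 1/3 with RR in seconds.

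The cost is at most two formula corrections and one confirmation. No visit, assessment or data collection changes.
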